2.8 Safety analyses

All safety analyses will be based on the safety set, except that the summary of safety data during the switched treatment period will be based on the Switch Analysis Set. All listings and tables will be presented by treatment group.

2.8.1 Adverse events (AEs)

AE summaries will include all AEs occurring during the on-treatment period (or the on-switched treatment period). All AEs collected in the AE eCRF page will be listed along with the information collected on those AEs e.g. AE relationship to study drug, AE outcome, etc. AEs with start date outside of the on-treatment period will be flagged in the listings.

AEs will be summarized by number and percentage of subjects having at least one AE, having at least one AE in each primary system organ class (SOC) and for each preferred term (PT) using MedDRA coding. A subject with multiple occurrences of an AE will be counted only once in the respective AE category. A subject with multiple CTCAE grades or the same preferred term will be summarized under the maximum CTCAE grade recorded for the event. AE with missing CTCAE grade will be included in the 'All grades' column of the summary tables.

In AE summaries, the primary system organ class will be presented alphabetically and the preferred terms will be sorted within primary SOC in descending frequency. The sorting order for the preferred term will be based on their frequency in the asciminib arm.

The following adverse event summaries will be produced by treatment arm for the Safety set and Switch Analysis Set: overview of adverse events and deaths, AEs by SOC and PT, summarized by relationship, seriousness, leading to treatment discontinuation, leading to dose interruption/adjustment, requiring additional therapy, and leading to fatal outcome. The study treatment-related AEs/SAEs/AEs leading to treatment discontinuation as well as SAE with fatal outcome are summarized for the Safety set and Switch Analysis set.

For posting to ClinTrial.gov and EudraCT, a summary table of on-treatment deaths and serious AEs and another summary table of non serious AEs by treatment, both including occurrences (an occurrence is defined as >1 day between start and prior end date of record of same preferred term) and sorted by SOC and PT, will be presented as well.

In order to account for differences in exposure between the treatment arms, incidence rates of AEs and SAEs will be presented by adjusting for duration of treatment period in patient-years. They will also be reported by time intervals (i.e. period of emergence: the event is assigned to the interval when it first started): 0 to 2 months, > 2 months to 6 months, > 6 months to 12 months, >12 months and more after the start of study treatment.

2.8.1.1 Adverse events of special interest / grouping of AEs

Data analysis of AESIs

An adverse event of special interest (AESI) is a grouping of adverse events that are of scientific and medical concern specific to compound asciminib. These groupings are defined using MedDRA terms, SMQs (standardized MedDRA queries), HLGTS (high level group terms), HLT (high level terms) and PTs (preferred terms). Customized SMQs (Novartis MedDRA queries, NMQ) may also be used. A NMQ is a customized group of search terms which defines a medical concept for which there is no official SMQ available or the available SMQ does not completely fit the need. It may include a combination of single terms and/or an existing SMQ, narrow or broad. The latest approved version of CRS prior to the respective database lock will be used.

For each specified AESI, number and percentage of patients with at least one event of the AESI occurring during the on-treatment period (or the on-switched treatment period) will be summarized.

Summaries of these AESIs will be provided by treatment arm (specifying grade, SAE, relationship, leading to treatment discontinuation, leading to dose adjustment/interruption, death, etc.). If sufficient number of events occurred, analysis of time to first occurrence will be applied.

A listing of all grouping levels down to the MedDRA PTs used to define each AESI will be generated.

2.8.2 Deaths

Separate summaries for on-treatment and all deaths (*including post-treatment deaths*) will be produced on the Safety set by treatment arm, system organ class and preferred term.

Similarly, a separate summary for on-switched treatment deaths will be produced on the Switch Analysis Set.

All deaths will be listed, where deaths occurring during the post-treatment, the on-switched treatment or post-switched treatment periods will be flagged. A separate listing of deaths prior to starting treatment will be provided for all screened subjects.

2.8.3 Laboratory data

Grading of laboratory values will be assigned programmatically as per National Cancer Institute (NCI) Common Terminology Criteria for Adverse Events (CTCAE) version 4.03. The calculation of CTCAE grades will be based on the observed laboratory values only, clinical assessments will not be taken into account. CTCAE Grade 0 will be assigned for all non-missing values not graded as 1 or higher. Grade 5 will not be used. Details of CTCAE grading and imputation rules are presented in [Appendix 5.3](#).

For laboratory tests where grades are not defined by CTCAE v4.03, results will be categorized as low/normal/high based on laboratory normal ranges.

On analyzing laboratory data, all sources (central and local laboratories) will be combined. The summaries will include all assessments available for the lab parameter collected no later than 30 days after the last study treatment administration date.

The following summaries will be produced on the Safety set separately for hematology and biochemistry laboratory data (by laboratory parameter and treatment):

- Worst post-baseline CTCAE grade (regardless of the baseline status). Each subject will be counted only for the worst grade observed post-baseline in the on-treatment period.
- Shift tables using CTCAE grades to compare baseline to the worst on-treatment value.
- For laboratory tests where CTCAE grades are not defined, shift tables using the low/normal/high/(low and high) classification to compare baseline to the worst on-treatment value.

The same summaries will be produced on the Switch Analysis Set for the on-switched treatment period.

The following listings will be produced separately for hematology and biochemistry for the laboratory data:

- Listings of all laboratory data, with CTCAE grades and classification relative to the laboratory normal range. Lab data collected during the post-treatment period will be flagged.
- Listing of all CTCAE grade 3 or 4 laboratory toxicities

Liver function parameters

Liver function parameters of interest are total bilirubin (TBL), Alanine aminotransferase (ALT), Aspartate aminotransferase (AST) and alkaline phosphatase (ALP). The number (%) of patients with worst post-baseline values as per Novartis DILI Clinical safety guidelines will be summarized for the criteria defined by single lab parameter. For combination of various parameters, the worst post-baseline values from each single parameter are taken into consideration, i.e. it may not come from the concurrent measurement (i.e. same assessment). :

The following summaries will be produced:

- ALT or AST > 3x upper limit of norm (ULN)
- ALT or AST > 5xULN
- ALT or AST > 10xULN
- ALT or AST > 20xULN
- TBL > 2xULN
- TBL > 3xULN
- ALT or AST > 3xULN & TBL > 2xULN
- ALT or AST > 3xULN & TBL > 2xULN & ALP \geq 2xULN
- ALT or AST > 3xULN & TBL > 2xULN & ALP < 2xULN

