2.8.4.4 Liver events

There are separate eCRF pages to collect acetaminophen/paracetamol, autoimmune, drug use 6 months prior to liver event, immunoglobulin, liver function tests, pathology, related imaging, viral serology and potential impact of alcohol use, and an overview eCRF page. Data on the overview eCRF page will be listed by treatment arm. Assessments collected during the post-treatment period will be flagged.

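### The combined liver rows pair worst values from different dates, so patients can be misclassified in either direction; time-linked rows should be added

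*Combined protocol and SAP*

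**What the plan says.** SAP section 2.8.3, under liver function parameters, plans three combined rows. The first has no ALP condition: "ALT or AST > 3xULN & TBL > 2xULN". The other two split it by ALP. One requires ALP of at least 2×ULN; the other is "ALT or AST > 3xULN & TBL > 2xULN & ALP < 2xULN".

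For all combined rows the rule is that "the worst post-baseline values from each single parameter are taken into consideration, i.e. it may not come from the concurrent measurement". The rule and the three rows are the same in amendment 3.0 (7 August 2020) and addendum 1.0 (14 October 2020). The section plans no version that needs the same sample or a fixed time window.

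On the time span: "The summaries will include all assessments available for the lab parameter collected no later than 30 days after the last study treatment administration date". Two listings stand beside the table. Section 2.8.3 has "Listings of all laboratory data, with CTCAE grades and classification relative to the laboratory normal range", and section 2.8.4.4 says of liver events: "Data on the overview eCRF page will be listed by treatment arm".

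**The concern.** Taking the worst value of each parameter separately is inclusive for conditions of the form greater than. For a condition of the form less than, it excludes. The SAP applies one rule to both without comment. If worst ALP means the highest value (implied but not stated), a single ALP of 2×ULN or more at any other on-treatment visit takes a patient out of the low-ALP row, even when ALP was low at the time ALT/AST and bilirubin rose together.

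The same rule also pairs an ALT/AST peak with a bilirubin peak on another date. That adds a patient with no concurrent event to the row without an ALP condition and to one of the two ALP rows.

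Both errors have more room to occur the longer a patient is observed. Under section 1.1, treatment continues to 96 weeks after the last patient's first dose, or 48 weeks after the last switch if that is longer, so early enrollees can be followed beyond 96 weeks. Section 2.8.1 provides for differing exposure between the arms and adjusts adverse event rates for it; this table has no such adjustment. Misclassification could therefore differ by arm. If the rows hold few patients, one patient in the wrong row alters how the table reads.

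**Working it through.** The plan states no expected liver count, event rate or threshold for action, so there is no figure to reproduce. The check is of the classification logic, then of the net error under stated assumptions.

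**Step 1. Hypothetical patients.** Values are multiples of ULN, in the order ALT, bilirubin, ALP. Results are in the order any ALP / ALP ≥ 2× / ALP < 2×. The SAP rule takes the maximum of each parameter; the alternative needs all conditions at one assessment.

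| Patient | Day 60 | Day 300 | SAP rule | Same assessment |
|---|---|---|---|---|
| A | 6, 3, 1.2 | 1, 0.8, 2.5 | yes / yes / no | yes / no / yes |
| B | 6, 0.8, 1.2 | 1, 3, 1.2 | yes / no / yes | no / no / no |
| C | 6, 3, 1.2 | 1, 0.8, 1.1 | yes / no / yes | yes / no / yes |
| D | 6, 0.8, 2.5 | 1, 3, 1.2 | yes / yes / no | no / no / no |

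Patient A is a concurrent low-ALP case placed in the high-ALP row. Patients B and D have no concurrent event but enter the table, B in the low-ALP row and D in the high-ALP row. Patient C is classified the same way by both rules.

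**Step 2. Net error in the low-ALP row.** Let T be the number of concurrent cases with low ALP at that time, F the number of patients whose ALT/AST and bilirubin elevations occur only at different times, and q the chance of ALP ≥ 2×ULN at some other on-treatment visit (for F, at any visit). All three are assumptions, with one q for both groups.

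- Expected count under the SAP rule: (T + F)(1 − q)
- Count under the same-assessment rule: T
- Error: (T + F)(1 − q) − T = F(1 − q) − Tq

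| T, F | q = 0.05 | q = 0.10 | q = 0.30 | q = 0.50 | Understated if q exceeds F/(T + F) |
|---|---|---|---|---|---|
| 1, 0 | −0.05 | −0.10 | −0.30 | −0.50 | 0 |
| 2, 1 | +0.85 | +0.70 | +0.10 | −0.50 | 0.33 |
| 1, 1 | +0.90 | +0.80 | +0.40 | 0.00 | 0.50 |
| 1, 2 | +1.85 | +1.70 | +1.10 | +0.50 | 0.67 |

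Put the other way, net understatement needs F/T below q/(1 − q). That is 0.05/0.95 = 0.05 at q = 0.05, and 0.10/0.90 = 0.11 at q = 0.10.

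**Step 3. The other rows.** The high-ALP row gains Tq + Fq. Adding the low-ALP error gives F(1 − q) − Tq + Tq + Fq = F. So, relative to a same-assessment rule, the row without an ALP condition can only be overstated (by F), never understated.

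**The case against.** The strongest reply is that this is an open screening convention: the SAP says plainly that the values need not be concurrent. No patient vanishes. Patient A remains in the row without an ALP condition and in the high-ALP row, and where ALP is available the two ALP rows add up to the first, so a reader can see that someone needs review. The laboratory values and the liver-event overview page are also listed. All of this stands, and it limits the seriousness of the point. It does not remove it, because neither listing derives whether the elevations coincided, and no listing is planned for just the patients who meet the combined criteria. For ECG, section 2.8.4.1 does plan a listing restricted to subjects with notable values.

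A reader might go further and infer that the low-ALP row is the key Hy's Law count and that the rule understates it. The documents do not support this. Section 2.8.3 neither uses that term nor calls the row key, and no decision rule depends on it. Step 2 shows that the net error can take either sign. No rate of high ALP and no expected case count is given; 5% to 10% for q is only an illustration.

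It might also be inferred that a late ALP value at any time would displace a case. It counts only if it falls on treatment or within 30 days of last dose. For patients who switch, section 2.1.1 ends the on-treatment period no later than the day before the first asciminib dose. The part of the document reviewed does not include the dose-modification section, so it cannot be assumed that a patient with such rises stayed on treatment long enough.

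**Conclusion.** The point holds as one of misclassification in both directions. Under the stated rule, and reading worst ALP as the maximum, a concurrent low-ALP case can move to the high-ALP row, and patients with no concurrent event can be counted in the row without an ALP condition and in one of the two ALP rows. For the low-ALP row the net effect ranges from −0.5 to +1.85 patients over the scenarios shown; its sign cannot be settled from the documents. This is a modest defect in a safety table. It is worth correcting because the remedy is cheap and time-linked rules already appear elsewhere in the SAP: corrected calcium uses calcium and albumin from the same assessment (section 5.3), and hematologic response combines laboratory results only within two weeks (section 5.4.3).

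**What to change.** - Keep the any-time row for ALT/AST > 3×ULN with bilirubin > 2×ULN, labelled as a screening row.
- For the 96-week and end-of-study-treatment analyses, derive the combination rows from ALT/AST and bilirubin elevated in the same sample, or within a window fixed in advance. Take ALP at that time for the split at 2×ULN. Say which assessment counts if a patient qualifies more than once.
- For the primary analysis, whose database is already locked, provide the same rows as a supplementary table.
- Wherever the any-time rule is kept, state that worst ALP means the maximum.
- List every patient in the any-time row with dated ALT, AST, bilirubin and ALP values.

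The cost is a short SAP amendment, a small amount of programming, one extra set of rows and one listing. No new data are needed.

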2.8.4 Other safety data

2.8.4.1 ECG and cardiac imaging data

12-lead ECGs including PR, QRS, QT, QTcF and RR intervals will be obtained centrally for each subject during the study. ECG data will be read and interpreted centrally.

The echocardiogram will be performed and evaluated locally to assess the left ventricular ejection fraction (LVEF).

Data handling

The average of the triplicate ECG parameters at each time point will be used in the analyses.

For unscheduled visits, ECGs that are reported on the same day and within 30 minutes apart from each other will be assumed to be sequential ECGs and thus will be used to compute the mean of the ECG parameters.

Unscheduled ECG measurements will not be used in computing the summary statistics for change from Baseline at each post-baseline time point. However, they will be used in the outlier analyses (e.g. QTc > 450 ms, > 480 ms, or > 500 ms at any time point, or an increase from Baseline in QTc > 30 ms or > 60 ms). End of treatment ECG measurements for discontinued patients will be considered as an unscheduled measurement in case it occurs outside a scheduled visit.

Data analysis

The number and percentage of subjects with notable ECG values will be presented by treatment arm for the Safety set and Switched Analysis Set. Notable values are defined below:

- QT, QTcF
 - New value of > 450 and \leq 480 ms
 - New value of > 480 and \leq 500 ms
 - New value of > 500 ms
 - Increase from Baseline of > 30 ms to \leq 60ms
 - Increase from Baseline of > 60 ms
- HR

- Increase from baseline >25% and to a value > 100 bpm
- Decrease from baseline >25% and to a value < 50 bpm
- PR
 - Increase from baseline >25% and to a value > 200 ms
 - New value of > 200 ms
- QRS
 - Increase from baseline >25% and to a value > 120 ms
 - New values of QRS > 120 ms

A listing of all ECG assessments will be produced by treatment arm and notable values will be flagged. A separate listing of only the subjects with notable ECG values will also be produced. In each listing the assessments collected during the post-treatment period will be flagged.

Change from baseline ECG parameters by timepoint will also be summarized by treatment.

A listing of all LVEF assessments will be produced by treatment arm. In the listing, the assessments collected outside of on-treatment period will be flagged.

A summary table by treatment arm with descriptive statistics for LVEF at different timepoints (baseline, week 20) and for change from baseline will be presented. A shift table for LVEF categories ($\leq 40\%$, 41-49%, $\geq 50\%$) at baseline versus worst value on treatment will also be presented.

2.8.4.2 Cardiovascular risk factor assessment

Prior to randomization and at the end of treatment, for each patient information of the following risk factors is collected: heavy smoking, low physical activity, unhealthy diet, and other. A listing by treatment arm will be presented.

Family medical history of each patient for ischemic heart disease, cardiac arrhythmia, sudden death, high cholesterol, diabetes mellitus, heart defects (congenital heart disease), and heart failure is also collected prior to randomization and at the end of treatment. A listing by treatment arm will be presented.

2.8.4.3 Vital signs

Vital sign assessments are performed in order to characterize basic body function. The following parameters were collected: height (cm), weight (kg), body temperature ($^{\circ}\text{C}$), heart rate (beats per minute), systolic and diastolic blood pressure (mmHg).

Data handling

Vital signs collected on treatment will be summarized. Values measured outside of on treatment period will be flagged in the listings.

Data analysis

The number and percentage of subjects with notable vital sign values (high/low) in systolic blood pressure, diastolic blood pressure, pulse rate, weight and temperature will be presented by treatment arm.

A listing of all vital sign assessments will be produced by treatment arm and notable values will be flagged. In the listing, the assessments collected outside of on-treatment period will be flagged.

2.8.4.4 Liver events

There are separate eCRF pages to collect acetaminophen/paracetamol, autoimmune, drug use 6 months prior to liver event, immunoglobulin, liver function tests, pathology, related imaging, viral serology and potential impact of alcohol use, and an overview eCRF page. Data on the overview eCRF page will be listed by treatment arm. Assessments collected during the post-treatment period will be flagged.

2.8.4.5 Pulmonary function tests

Data of pulmonary function tests will be listed by treatment arm. Assessments collected during the post-treatment period will be flagged.

2.8.5 Additional Analyses

2.8.5.1 ECOG performance status

ECOG performance status collected on treatment will be summarized. Shift tables will be provided comparing baseline with best and worst values during study for each treatment group.

2.9 Pharmacokinetic endpoints

PK parameters

The PK parameters that will be determined are shown in [Table 2-7](#). The PK parameters for asciminib are derived based on the non-compartmental methods using Phoenix WinNonlin[®] software version 6.4 in patients with full PK sampling in PAS.

Table 2-7 Non-compartmental PK parameters for asciminib in full PK group

AUC0-12h	The area under the plasma concentration-time curve from time zero to 12 hours ($\text{ng}\cdot\text{hr}\cdot\text{mL}^{-1}$)
AUClast	The AUC from time zero to the last measurable plasma concentration sampling time (T_{last}) ($\text{ng}\cdot\text{hr}\cdot\text{mL}^{-1}$)
Ctrough	Trough plasma concentration (measured concentration at the end of a dosing interval at steady state [taken directly before next administration])
Cmax	The maximum (peak) observed plasma concentration after dose administration (ng/mL)
Tmax	The time to reach maximum (peak) plasma concentration after dose administration (hr)
Tlast	The time to reach the last measurable plasma concentration after dose administration (hr)
CL/F	The total apparent body clearance of drug from the plasma after oral administration ($\text{L}\cdot\text{hr}^{-1}$)

Descriptive statistics (n, arithmetic mean, CV% mean, standard deviation (SD), median, geometric mean, CV% geo-mean, minimum and maximum) will be presented by treatment for PAS for all PK parameters defined in [Table 2-7](#) except Tmax, where only n, median, minimum and maximum will be presented.

All individual PK parameters will be listed for patients treated with asciminib and with full PK sampling in the safety set.

PK concentrations

Descriptive statistics (n, m (number of non-zero concentrations), arithmetic mean, CV% mean, SD, median, geometric mean, CV% geo-mean, minimum and maximum) for asciminib concentration will be presented at each scheduled time point for the PAS.

The mean (\pm SD) and geometric mean concentration-time profiles for asciminib over time will be displayed graphically for PAS on the linear and semi-log view (Week 2 Day 1; for patients with full PK sampling only).

The mean (\pm SD) and median Ctrough values of asciminib over time will be displayed graphically for PAS on the linear scale only (Patients with full and sparse PK sampling).

All individual plasma asciminib concentration data will be listed for patients treated with asciminib in the Safety Set.

Handling of PK data below LLOQ or missing

All concentration values below the lower limit of quantitation (LLOQ, 1 ng/mL) are set to zero by the Bioanalyst, and will be displayed in the listings as zero and flagged. LLOQ values will be treated as zero in any calculations of summary statistics, and treated as missing for the

calculation of the geometric means and their CV%. The number of non-zero concentrations will also be reported in the summary statistics.

Missing values for any PK data will not be imputed and will be treated as missing.

